15.2.	Informed Consent Form.....	343
15.3.	Risks and Procedures to Minimize Risk.....	343
16.	Quality Assurance and Quality Control	35
16.1.	Auditing.....	354
16.2.	Monitoring.....	34
16.3.	Data Management.....	354
17.	References.....	37
18.	Appendix 1: Questionnaires.....	40

1. List of Abbreviations

ADA	Anti-Drug Antibodies
ADR	Adverse Drug Reaction
AE	Adverse Event
ALT	Alanine aminotransferase
ANOVA	Analysis of Variance
AST	Aspartate aminotransferase
BMI	Body Mass Index
BPM	Beats per minute
BUN	Blood urea nitrogen
CBC	Complete Blood Count
CRF	Case Report Form
CTMS	Clinical Trial Management Software
Cl	Chloride
Cr	Creatinine
eCRF	Electronic Case Report Form
EDTA	Ethylenediaminetetraacetic acid
ET	Early Termination
GCP	Good Clinical Practices
GLP	Good Laboratory Practices
GMP	Good Manufacturing Practices
GGT	Gamma glutamyl transpeptidase/transferase
h or hr	Hour
HCT	Hematocrit
Hb	Hemoglobin
HIV	Human Immunodeficiency Virus
ICF	Informed Consent Form
ICH	International Council for Harmonisation
ID	Identification
IP	Investigational Product
IRB	Institutional Review Board
IUD	Intrauterine Device
K	Potassium
Kg	kilogram
m	Meter
MCH	Mean corpuscular hemoglobin
MCHC	Mean corpuscular hemoglobin concentration
MCV	Mean corpuscular volume
Na	Sodium
NCS	Not clinically significant
OTC	Over the counter
PD	Protocol Deviation
PI	Principal Investigator
PV	Protocol Violation
RBC	Red Blood Cell
SAE	Serious Adverse Event

SAP	Statistical Analysis Plan
SOP	Standard Operating Procedure
WBC	White Blood Cell
EDA	Exploratory Data Analysis

2. Protocol Synopsis

Title: A randomized, double-blind, controlled, single-centre, 21-day study to investigate the efficacy of AllerPops to reduce nasal symptoms in adult volunteers with seasonal/year-long nasal allergies.

Phase: Phase II

Duration: Up to 30 days between Screening (V1) and Baseline (V2), and a 21-day intervention period, with dosing occurring every other day for a minimum of 3 doses, and thereafter until the participant is satisfied with the relief of the nasal allergy symptoms. The suitable season for the trial will be determined based on the seasonal variation measures.

Primary Objectives: To assess the effectiveness of AllerPops on relieving nasal symptoms compared to the control group in volunteers with seasonal/year-long allergies during the first 7 days of the 21-day intervention period.

Secondary Objective:

1. To evaluate the safety of AllerPops administration in volunteers with seasonal/year-long allergies during a 21-day intervention period.
2. To assess the duration of effectiveness of AllerPops in relieving nasal symptoms compared to the control group in volunteers with seasonal/year-long allergies during a 21-day intervention period (exploratory).
3. To evaluate the effect of the AllerPops administration on the oral microbial presentation/microbiota using Amplicon Metagenomics Sequencing test through saliva samples during a 21-day intervention period (exploratory).
4. To evaluate the effect of the AllerPops administration on the IgE (total) blood level during a 21-day intervention period (exploratory).

Study Population: Seventy-two participants with seasonal/year-long nasal allergies.

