6.4 Directions

IMPORTANT: Must be fasting for at least 4 hours before taking the study product.

Directions for the Investigational Group:

1. Brush teeth with tap water (no toothpaste).
2. Scrub tongue with disposable tongue scraper provided. (**Caution:** *reaching too far may cause a gag reflex.*)
3. Gargle and swish hot (optimal 120°F) water for 10-20 seconds. Spit out and repeat gargling over the next 5 minutes. The tongue should be red and without any biofilm. If it is not, repeat *Step 2*, and gargle once more.
4. Self-administer one lozenge. Let the lozenge slowly melt in the mouth. Do not chew or swallow whole. This may take up to 60 minutes. Discard if it is not fully dissolved after 60 minutes. Wait at least 30 minutes before eating your next meal.
5. Repeat *Step 1* to *Step 5* every other day for a minimum of 3 doses.
6. After the 3rd dose, you may repeat *Step 1* to *Step 5* every other day until you are satisfied with the symptom relief up to and including Day 13. Do not take the product on Day 14 onwards and return all remaining product at Visit 4.

Directions for the Control Group:

1. A box containing 8 units of the Investigational Product will be dispensed. This box will only be dispensed once, at visit 2.
2. Microwave: heat the product in 5 second increments until soft. (Caution: more than 10 seconds of microwaving the product may cause it to burn).
3. Cut: cut the product into smaller pieces those are the size of your usual medication/supplement.
4. Swallow: Participant will be instructed to swallow each of the small pieces over time with plenty of warm water. The participant will also be allowed to have a few sips of water to moisten the mouth and throat prior to swallowing the control product, if they feel it is necessary. Wait at least 30 minutes before eating your next meal. For next 2 doses, you must repeat *Step 2* to *Step 4* once every other day (day 3 and day 5).
5. After the 3rd dose, you may choose to use additional doses until you are satisfied with the symptom relief. If you choose to continue using the product, you must repeat *Step 2* to *Step 6* once every other day up to (and including) day 13. Maximum dose expected during day 1 to 13 is 7. Do not take the product on day 14 onwards and return all remaining product at visit 4.

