6.5 Randomization

[figure not shown]
After eligibility for participants has been confirmed, they will be allocated to a study arm (Investigational or control). Participants will then be randomized accordingly to ensure an equal and unbiased distribution of products. The master randomization list will only be accessible to the designated unblinded personnel at the site until the database is locked. Participants will be given an envelope containing a detailed dosing instruction sheet. They will be instructed to take this home and open it, read and understand the procedure, and contact the site if they have any questions. The contact information for the site will be that of the designated unblinded personnel – these individuals will be able to answer any questions the participants may have about their assigned dosing instructions. Participants will be asked to not disclose information about their assigned dosing instructions to any study staff except the unblinded personnel whose contact information is contained in the detailed dosing instruction sheet.

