6.6 Blinding and Unblinding

Blinding of study products will be maintained by appropriately delegated study staff. Designated unblinded personnel will randomize the groups using block randomization ensuring an equal distribution in each group. All site staff (excluding designated unblinded personnel) will remain blinded throughout the study until the data-lock and study-closeout stage.

Since both groups will be receiving identical products (with different instructions of use for each group), emergency unblinding will not be applicable to this trial.

7. Study Design (Flow chart)

8. Planned Study Visits

Pre-Screening Telephone Call:

Potential participants who will be contacted to participate in this study will be pre-screened over the phone. They will be asked a series of questions about their health and lifestyle. As part of that telephone pre-screening the following questions will be asked regarding their allergy symptoms:

- 1- How do you score your nasal congestion (0-5, with 5 being the worst)?
- 2- How do you score your Nasal Discharge or sneezing (0-5, with 5 being the worst)?
- 3- How do you score your watery or itchy eyes (0-5, with 5 being the worst)?
- 4- How many times do you brush your teeth a day (0-3, 0,1,2,3 or more)?
- 5- How many times do you use mouthwash a day (0-2, 0,1,2 or more)?
- 6- How many times do you floss your teeth a day (0-2, 0,1,2 or more)?

Scoring Standards: Total score ≥ 7 in question 1-3 and Total score ≤ 4 in question 4-6 will be booked for Screening (V1). Potential participants with a total score of < 7 in question 1-3 and/or total score > 4 in question 4-6 will not pass the telephone pre-screening and will not be booked for Visit 1.

Visit 1 – Screening

Participants will not be required to fast prior to this visit. The delegated study staff will present the ICF, and review its contents with the participant. The study staff will answer any questions the participant may have.

The Informed Consent Form (ICF) will be provided to the participant. After a sufficient period of reflection, the written and informed consent of the participant will be sought. Each page of the ICF will be initialed and the last page will be signed by the participant. Once signed and attested to by the PI or delegate, a copy of the signed original ICF will be provided to the participant.

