11.3. Analysis Plan

11.3.1. Primary Variables

- The Total Nasal Symptoms Score (TNSS) change from the screening (V1), baseline by comparing D1(V2) and D7(V3) for each group and the differences between groups (investigational and control) will be statistically assessed.
- Peak Nasal Inspiratory Flow (PNIF) values change from the baseline by comparing D1 and D7 for each group and the differences between groups (investigational and control) will be statistically assessed.

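### The title says double-blind and promises the efficacy of AllerPops, but participants know their procedure and self-rate TNSS, and both arms take the same lozenge

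*Combined protocol and SAP*

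**What the plan says.** **Masking.** The title in section 2 describes "A randomized, double-blind, controlled, single-centre, 21-day study to investigate the efficacy of AllerPops to reduce nasal symptoms". Section 6.6 defines who is masked: "All site staff (excluding designated unblinded personnel) will remain blinded throughout the study". Participants are not mentioned there as masked. Section 6.5 gives each participant an envelope with the dosing sheet: "They will be instructed to take this home and open it, read and understand the procedure". It then relies on their discretion: "Participants will be asked to not disclose information about their assigned dosing instructions to any study staff except the unblinded personnel".

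**Procedures.** In section 6.4 the investigational group brushes, scrapes the tongue and gargles hot water, and then: "Let the lozenge slowly melt in the mouth. Do not chew or swallow whole". The control group microwaves the product and cuts it up, and then: "Participant will be instructed to swallow each of the small pieces over time with plenty of warm water". Section 6.6 acknowledges the difference: "Since both groups will be receiving identical products (with different instructions of use for each group), emergency unblinding will not be applicable".

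**Outcome.** Section 11.3.1 lists as a primary variable "The Total Nasal Symptoms Score (TNSS) change from the screening (V1), baseline by comparing D1(V2) and D7(V3) for each group", together with Peak Nasal Inspiratory Flow (PNIF). The TNSS form in Appendix 1 is completed by the participant and covers the preceding week.

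**Contrast.** Section 3 says that controls take the same product, swallowed and without mouth cleaning, and that the control arm is there to support the effect of the whole two-step method. The primary objective in sections 2 and 4 is worded as the effectiveness of AllerPops compared with the control group.

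**The concern.** The label and the objective determine how the result will be read. As they stand, a significant TNSS difference could be reported as double-blind evidence that AllerPops works. The design supports a narrower statement: one way of using the lozenge did better than another, as rated by people who knew which way they had used it.

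Replacing the label with an unqualified statement that site staff were blinded would not be safe either, because parts of the protocol leave staff masking open.

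**Working it through.** **1. Who knows the procedure.** Setting the sections side by side:

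- Participant: reads the sheet (6.5) and performs the steps (6.4). The two routines cannot be mistaken for each other, so the participant knows the procedure.
- Designated unblinded personnel: know it by design (6.5, 6.6).
- Other site staff: intended to be masked (6.6). This holds only if participants do not tell them (6.5).
- Person rating TNSS: the participant (Appendix 1). TNSS is therefore not rated blind to procedure.

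**2. What is left open.**

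- Section 6.3 puts written instructions for use in the consent form, while 6.5 delivers the assigned instructions in an envelope after allocation. Whether the consent form shows one procedure or both is not stated. If it shows both, participants see the contrast before they are randomised.
- Visit 2 (section 8) supplies the product and, where applicable, an oral hygiene kit. Mouth cleaning belongs to the investigational arm only (sections 3 and 6.4), so the kit could reveal the arm to whoever hands it over or sees it. No section reserves that task for unblinded personnel.
- Neither section 8 nor 9.6 says who takes the PNIF measurement.
- No section says whether participants are told which method is the investigational one.

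**3. What the comparison estimates.** Let μ be the mean change without the lozenge, A the effect of the swallowed lozenge relative to none, and M the further effect of two-step use relative to swallowing.

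- Investigational arm: μ + A + M
- Control arm: μ + A
- Difference: (μ + A + M) − (μ + A) = M

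A cancels. The effect of AllerPops against no AllerPops is A + M in the investigational arm and A in the control arm, and neither can be estimated. M combines mouth cleaning with oral dissolution, which always change together. On TNSS the observed difference is M + b, where b is any difference in rating that comes from knowing the procedure. The trial cannot separate b from M.

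**4. Illustration of b (assumed values only).** The documents give no figure for b. The only related input is N = 72 in section 11.1, which is 72/2 = 36 per arm under equal allocation (6.6). With d = 0.6 and 80% power, a t test at 0.05 needs 35.04, rounded up to 36 per arm (72 in total), one-sided, and 44.59, rounded up to 45 per arm (90 in total), two-sided. The stated 72 thus matches the one-sided calculation. The readable text gives no sidedness and Figure 1 is not shown, so both are given below.

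Assume M = 0 and b in SD units. The noncentrality is b × √(36/2) = b × √18, with 70 degrees of freedom; for b = 0.2 it is 0.2 × 4.243 = 0.849.

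| Assumed b (SD) | Favours investigational, two-sided 0.05 (nominal 2.5%) | Favours investigational, one-sided 0.05 (nominal 5%) |
|---|---|---|
| +0.1 | 6.2% | 11.0% |
| +0.2 | 13.1% | 21.1% |
| +0.3 | 24.1% | 35.0% |
| −0.2 | 0.3% | 0.7% |

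The conclusion does not depend on this table.

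**The case against.** **Knowing the procedure is not knowing the hypothesis.** Both arms take the same active lozenge, neither is a placebo, and the dosing sheet and consent text are not available to us. Participants may not know which method is favoured. This stands, and it rules out an inference a reader might draw: that TNSS is biased towards the investigational arm. The documents establish neither the direction nor the existence of such a bias. They also describe no masking to the hypothesis, so this possibility does not rescue the label.

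**The contrast is disclosed.** Section 3 defines the control openly just before the objectives in section 4, section 6.6 repeats that the products are identical, and the objective is relative to the control group. This also stands. A reader might infer that the sponsor hides the comparison; the text does not support that. What remains is a mismatch: the title and primary objective, which frame the conclusion, claim something that the comparison cannot estimate.

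**PNIF is a measured flow.** The self-rating concern does not carry over to it directly, although participants perform it knowing their procedure. But section 11.1 only applies p < 0.05 to every test, and no section requires PNIF to agree with TNSS. One also cannot assert that PNIF is taken by masked staff, since no section says who takes it.

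**The remedy is only wording and handling.** It changes no analysis and removes no bias. That is so, but it changes what may be concluded.

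**Conclusion.** The point holds, and the wording must be corrected. Double-blind is contradicted by sections 6.4 to 6.6: participants know their procedure and rate one of the two primary variables themselves. Masking is intended for site staff other than the designated unblinded personnel. It depends on non-disclosure and may be compromised by the kit at Visit 2. One might infer that staff masking fails; the documents show only that it is not secured.

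The trial can compare two-step use with swallowing without mouth cleaning, and nothing in this point makes that randomised comparison invalid in itself. It cannot show an effect of AllerPops against no AllerPops. That follows from the same lozenge being in both arms and needs no numerical assumption.

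The consequence is a narrower claim. The percentages under the assumed shifts only illustrate how the TNSS test would respond and carry no weight in this conclusion.

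**What to change.** 1. **Title and 6.6.** Remove double-blind. State in the title or in 6.6 that participants know their assigned procedure and that masking is intended for site staff other than the designated unblinded personnel.
2. **Reconcile 6.3, 6.5, 6.6 and Visit 2 in section 8.** Say in 6.6 whether the consent form shows one procedure or both. Have the already designated unblinded personnel hand over the product and kit, and have masked staff take PNIF. Reports may say that PNIF was measured by masked staff only if this was done. They must say that TNSS was self-rated by participants who knew their procedure.
3. **Primary objective (sections 2 and 4) and the report's conclusion.** Word the contrast as AllerPops used by the two-step method against the same lozenge swallowed without mouth cleaning. Draw no conclusion about AllerPops against no AllerPops.
4. **Participant-facing material.** Keep it neutral about which method is favoured, so that the new wording does not itself create expectation.

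Cost: a protocol amendment, which section 13 makes subject to regulatory approval before implementation and of which section 15.1 requires the IRB to be notified; a defined split of tasks between masked and unblinded staff; and a narrower claim. Sample size and visits do not change. Any expectation bias in TNSS remains.

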2.1. Inclusion Criteria

Participants must meet all of the following criteria to be considered eligible for admission to the study.

1. Participants will be clinically diagnosed with persistent or intermittent allergic rhinitis, according to the Allergic Rhinitis and Its Impact on Asthma (ARIA) classification. (The guidelines of Allergic Rhinitis and its Impact on Asthma (ARIA) group, classified it to intermittent (less than 4 days per week and for less than 4 weeks) and persistent (more than 4 days per week or lasting more than 4 weeks regardless of the number of days per week).
2. Male or female seasonal/year-long nasal allergy sufferers (as assessed by a questionnaire at screening) between the ages of 18 and 70.

3. Females who are not of childbearing potential (post-menopausal defined as those with amenorrhea for at least 2 years). Females of childbearing potential should be either sexually inactive (abstinent) for 60 days prior to the first dose of the study, throughout the study and for 30 days after completion of the study, or be using one of the following acceptable methods of birth control:
 - i. Surgically sterile (bilateral tubal-ligation, hysterectomy, bilateral oophorectomy) for at least 90 days prior to the first dose of the study.
 - ii. IUD in place for at least 60 days prior to the first dose of the study, throughout the study and for 30 days after completion of the study.
 - iii. Barrier methods (condom, diaphragm) with spermicide for at least 60 days prior to the first dose of the study, throughout the study and for 30 days after study completion.
 - iv. Hormonal contraceptives for at least 90 days prior to the first dose of the study, throughout the study, and for 30 days after study completion.

*Changes to the method of birth control while participating in the study will be judged by the PI for acceptability.

4. Written informed consent obtained and signed by participant.
5. BMI between 18.5 and 29.9 kg/m², with a stable weight over the last 3 months. (A stable weight is defined as <5% of total body weight change in the last 3 months).
6. Agrees not to use any over the counter, prescription, health supplement or dietary supplement from at least 14 days prior to screening until the end of the study.
7. Agrees to maintain current dietary habits, level of physical activity, occupational and living environment for the trial duration.
8. Does not regularly consume more than 2 standard* alcoholic beverages a day as assessed through verbal confirmation at screening, and agrees not to consume >2 standard* alcoholic beverages per day for the trial duration.
9. Non-smoker within 12 months prior to dosing as assessed by verbal confirmation.
10. Stable medical conditions that do not require medication use routinely and do not affect or involve the immune systems as determined by medical history, physical examination, clinical chemistry performed at screening, and as assessed by the Principal Investigator.
11. Agrees not to use nasal steroid spray from at least 14 days prior to screening until the end of the study.
12. Agrees not to use neti-pot and oil-pulling for at least 7 days prior to screening until the end of the study.
13. .
14. Have access to a microwave.

* A standard alcoholic beverage is defined as 12 ounces of beer, 5 ounces, of wine, or 1.5 ounces of liquor

2.2.Exclusion Criteria

Participants meeting any of the following criteria will not be eligible for admission to the study:

1. Participants who are pregnant/lactating or planning to become pregnant during the course of the clinical trial.
2. Participants who have any signs of active or recurrent upper airway infection (bacterial/viral).
3. Participants who have a known sensitivity or allergy to any of the study products, or ingredients.
4. Participation in another research study within 30 days prior to enrollment in this clinical trial.
5. Participants who are not able to tolerate venipuncture and/or have poor venous access.
6. Participants dependent on decongestants (nasal or oral) or receiving allergen-specific immunotherapy.
7. Participants who have been diagnosed with other clinical forms of rhinitis such as infectious rhinitis, rhinitis of pregnancy, food and alcohol-induced rhinitis, atrophic rhinitis, vasomotor rhinitis, rhinosinusitis and age-related rhinitis.
8. Participants who have receive previous acupuncture treatment or alternative medicine for AR in the last three months or planned in the next two years.
9. Participants who have received allergy desensitization therapy (current, during the past two years, or planned in the next two years).
10. Participants who have had any major surgery within 1 year of enrollment into the clinical trial or have any anticipated major surgeries intended to occur during the clinical trial.
11. Participants who have received a blood transfusion within 8 weeks of enrollment in the clinical trial.
12. Participants who have donated blood or plasma to a blood bank or clinical study within 8 weeks of enrollment and during the study except venipuncture as part of clinical trial.
13. Participant has known severe medical conditions, such as cardiovascular, liver or renal dysfunction, diabetes mellitus, cancers, cerebrovascular diseases, blood system diseases which in the opinion of the Principal Investigator, may preclude safe study participation, or interfere with study objectives.
14. Participants who are immunocompromised or have been diagnosed HIV/AIDS, Hepatitis B, or untreated Hepatitis C.
15. Participant has a history of alcohol or drug addiction treatment within the last 2 years prior to inclusion in the study, or any current addiction on alcohol or drugs.
16. Participants with Grade II or III septum deviation and/or presence of nasal polyps or other conditions that lead to nasal obstruction.
17. Participant has any other medical, social or other condition that, in the opinion of the Principal Investigator, would make participation in the study unsafe, complicate interpretation of study outcome data, or otherwise interfere with achieving the study objectives.
18. Participants with allergic asthma and/or moderate to severe atopic dermatitis.
19. History of anaphylactic reactions.

20. Participants with any risk of developing dental cavity or on-going oral health issue, as assessed during their regular dentist visit in past 6 months.
21. Participants who brush more than twice a day and/or mouthwash more than once a day and/or floss more than once a day.

